- (3) If less than small effects emerge for both the between-group effects on the early mechanism slope *and* for the time effect (i.e., average slope), this would be interpreted to indicate a lack of early change (in any treatment condition) on the mechanism variable. In this instance, that mechanism variable would not be tested in a subsequent SEM. If *either* of the effect sizes are equal to or larger than 0.01 (indicating a small or larger time effect, on average) or a small or large Group X Time effect emerges (indicating at least a small group effect on early change in mechanism), then we will proceed to Step 2 for that mechanism variable.

Step 2. Test the model presented in Figure 3 for any mechanism variable that met the Step 1 conditions described above.

- (4) First paths a_1 and a_2 will be tested. The a_1 and a_2 coefficients represent the strength of the predictive relationships from the two dummy IVs¹ to early treatment slope in catastrophizing (i.e., to evaluate the impact of treatment condition on early treatment changes in catastrophizing). Together, these tell us if treatment condition had a direct effect on the early treatment slope in the mechanism variables. If both of these coefficients are non-significant (consistent with the Shared Mechanisms Model) they will be eliminated from the final SEM. If either or both of these pathways are statistically significant, this will be interpreted to mean that there is a between-treatment condition difference in early change in the mechanism variable being evaluated, and these effects will be retained in the model.
- (5) In the case of at least one statistically significant a coefficient, we will perform planned post-hoc ANOVA models for each of the three treatment groups to understand these differences and to determine if the findings are consistent with the Specific Mechanisms Model. For example, if catastrophizing is uniquely targeted by CT, we would anticipate a significant treatment condition effect (in either or both of the two a coefficients) on early catastrophizing slope, with post hoc tests indicating larger pre- to mid-treatment decreases in catastrophizing for the CT condition than the MM or AS interventions. However, the full test of the Specific Mechanisms Model also takes into account the b path, described below.

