¹ In the proposed SEM, treatment condition (i.e., which of three treatments the participant is assigned to) is represented by two variables: "CTvsOther" (coded as "1" if the participant is assigned to the CT condition, "0" if not) and "MMvsOther" (coded as "1" if the participant is assigned to the MM condition, "0" if not). These two dummy variables are exogenous and have a correlation of $r = .50$ (if groups are of equal size). When considered in the same model (i.e., when controlling for the other), the two variables contain information about all three treatment conditions.

[figure not shown]
(6) In order to establish a mechanism effect on outcome (i.e., that cognitive content, cognitive process, or activity level predicts subsequent change in pain interference) we will next test for significance of the *b* coefficients. We will test the *b* coefficient for significance across each of the three mechanism variables (i.e., three significance tests, one per SEM model). Any *b* coefficients that are not significant indicate that early change in that mechanism variable is not associated with late change in pain interference, indicating a lack of support for it as a mechanism variable in treatment. A significant *b* coefficient will be interpreted as evidence supporting early treatment change in the mechanism variable in question as explaining late treatment change in pain interference.

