As indicated, up to three SEMs (one for each mechanism) will evaluate and test for significance of the *a* and *b* coefficients for each mechanism variable that met the Step 1 assumptions described above (i.e., that evidenced at least a small early slope or larger, for at least one of the treatments). The combination of a treatment effect on the mechanism variable (coefficient *a*) and a significant *b* coefficient for a particular mechanism variable (indicating that early change in the mechanism variable predicts a late change in outcome), with *post hoc* tests linking each treatment to its targeted mechanism variable (i.e., CT, MM, and AS having the largest effects on cognitive content, cognitive process, and activity level, respectively) would support the Specific Mechanisms Model. A significant *b* coefficient in light of non-significant *a* coefficients (i.e., the mechanism plays a role in outcome, but all three treatments have a similar impact on the mechanism variable) would support a Shared Mechanisms Model. Thus, together, the significance levels of the *a* and *b* coefficients will address the study aims. In short, the results of the (maximum) six planned statistical tests (i.e., whether or not there are between-group differences in the three early mechanism slopes, and the significance level of the three *b* coefficients) will allow us to evaluate if the three mechanism variables play a role in treatment outcome, and whether this role is shared between the treatments or unique to a subset of them.

Exploratory Moderation Analyses

We also plan to conduct a preliminary test of the LAE model. Specifically, SEM will be used to evaluate the extent to which baseline catastrophizing, activity levels, and non-judgment are respectively associated with response to CT, AS, and MM. Figure 4 below illustrates the statistical approach that we propose to use to evaluate the LAE model. For illustrative purposes, only the role of baseline catastrophizing moderating response to treatment is depicted. As per the above models, the treatment condition variable is represented by two variables: "CTvsOther" (coded as "1" if the participant is assigned to the CT condition, "0" if not) and "MMvsOther" (coded as "1" if the participant is assigned to the MM condition, "0" if not). When considered in the same model (i.e., when controlling for the other), the two variables contain information about all three treatment conditions.

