Figure 4. SEM model evaluating the "Limit" component of the LAE model

In the model depicted in Figure 4, while significant change in outcome from pre- to post-treatment is expected, it is anticipated that the effect of treatment condition on outcome will be non-significant (i.e., we anticipate that all three treatments will be associated with similar pre- to post-treatment improvements in pain interference, as reflected by non-significant a_1 and a_2 coefficients). However, the LAE model predicts that the post-treatment pain interference score, when controlling for pre-treatment pain interference, will be significantly associated with baseline levels of pain catastrophizing (i.e., path b in the model). We will also test the b coefficient for significance across each of the three moderating variables. The extent to which the effect of the baseline moderator variable predicting outcome varies as a function of treatment will then be evaluated (i.e., the c_1 and c_2 coefficients in Figure 4). These two pathways from condition to path b in the model, when combined and examined as a single parameter, if significant, will indicate the presence of a Treatment \times Moderator interaction. In the event that this interaction effect is identified, post hoc tests will be conducted separately for each treatment condition. Continuing with the example shown in Figure 4, if baseline catastrophizing is found to be negatively associated with subsequent outcome, and this effect is stronger in CT than in MM and AS, then this will be interpreted as lending support for the predictions made with respect to the “Limit” component of the LAE model.

Additional Exploratory Analyses

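### The Step 2 rule reads two non-significant contrasts with AS as similarity of all three treatments, and it is not the single between-group test that the plan counts

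*Combined protocol and SAP*

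**What the plan says.** Section A2a, Hypothesis 1b, describes the Shared Mechanisms Model as treatment effects on early mechanism change that are both small and non-significant.

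Section D6s, Step 2, turns this into a rule. Item (4) says of the two treatment paths: "If both of these coefficients are non-significant (consistent with the Shared Mechanisms Model) they will be eliminated from the final SEM". The opposite branch is: "If either or both of these pathways are statistically significant, this will be interpreted to mean that there is a between-treatment condition difference". Item (5) makes further comparisons conditional: "In the case of at least one statistically significant a coefficient, we will perform planned post-hoc ANOVA models". After item (6), the plan says that a significant b with non-significant a's (the mechanism matters, "but all three treatments have a similar impact on the mechanism variable) would support a Shared Mechanisms Model"), and that "the significance levels of the *a* and *b* coefficients will address the study aims". That paragraph counts six tests: three b coefficients, and for each mechanism "whether or not there are between-group differences in the three early mechanism slopes". Section D6u orders six significance levels for alpha control.

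Footnote 1 defines one dummy for CT and one for MM and adds: "When considered in the same model (i.e., when controlling for the other), the two variables contain information about all three treatment conditions". In the exploratory moderation analysis the corresponding pair, c1 and c2, is tested "when combined and examined as a single parameter". No such statement is made for a1 and a2.

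Step 1 item (1) does contain an effect-size reading: a between-group eta squared below 0.01 is taken as a similar effect of the three treatments. Its stated use is to decide whether a mechanism goes forward to the SEM.

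**The concern.** There are three linked problems.

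1. **A null result becomes a positive finding.** Hypothesis 1b's requirement that effects be small is lost between the hypothesis and the rule. The Shared verdict needs only non-significant a's and a significant b, so it can be reached when the data are compatible with differences larger than the plan's own threshold for small.
2. **The verdict depends on the reference arm.** With both dummies in the model, both paths are contrasts with AS. CT versus MM is examined only if one of those contrasts is already significant.
3. **The alpha control is not defined.** The either/or rule gives two a p-values per mechanism, so 3 × 2 + 3 = 9 with the b tests, not six. The plan does not say which of them enter the ordering.

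At stake is the primary conclusion: a Shared Mechanisms result could be reported where the trial has only failed to show a difference.

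**Working it through.** **Inputs from the plan.** 240 completers, 80 per arm (D6u); dummy coding (D6s, footnote 1); Step 1 cut of eta squared 0.01; Table 5 alphas from 0.050 to 0.008, power 0.80, r = 0.30 for paths a and b, f² = 0.15 for the other three rows.

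**Assumptions.** Normal slopes with equal SDs; pooled variance on 240 − 3 = 237 df; two-sided alpha 0.05 before multiplicity control; complete data; no clustering or covariates. Differences are in slope-SD units. The plan gives no such differences, so a range is shown.

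**Table 5 first.**
- Mediation rows (joint significance, power for r = 0.30 squared ≥ 0.80): 111/131/142 by Fisher z or 107/126/138 by t, against the printed 109/129/140. These agree closely.
- Treatment-condition rows (noncentral F, λ = 0.15n, alphas as printed): 93/98/102 with 2 numerator df, exactly as printed. One df gives 77/82/85 and three give 104/109/114.

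The sample-size table therefore assumes one 2-df test per mechanism. Those rows are labelled as Treatment Condition × Mediation effects, so this supports a joint test being intended but does not prove it.

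**What the paths estimate.** With both dummies entered, a1 = CT − AS and a2 = MM − AS. The estimates share the AS mean and correlate at +0.5 with equal arms.

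**How often both a's are null** (400,000 simulated trials per row):

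| True pattern | Both a's null | 2-df test null |
|---|---|---|
| CT or MM alone differs by 0.5 SD | 10–11% | 9% |
| AS alone differs by 0.5 SD | 4% | 9% |
| CT or MM alone differs by 0.3 SD | 50% | 52% |
| AS alone differs by 0.3 SD | 36% | 52% |
| CT and MM 0.5 SD apart, AS midway | 36% | 19% |
| Arms equal | 91% | 95% |

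For one arm at 0.3 SD, the variance of the three means is (0.2² + 0.1² + 0.1²)/3 = 0.02, so eta squared = 0.02/1.02 = 0.0196, about twice the Step 1 cut. When CT alone differs by 0.3 SD, 14.5% of all trials have both a's null while CT versus MM, which would not be examined, is itself significant at 0.05.

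The last row gives the size of each rule: 9% against 5%. At alpha 0.0083, the strictest Table 5 tier, it is 1.6% against 0.8%.

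The Shared verdict also needs a significant b. At r = .30 and n = 240 (Fisher z), power for b is 0.997 at alpha 0.05 and 0.983 at 0.0083, so b filters out very little.

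**Step 1 against Step 2.** The 2-df test reaches p < 0.05 at F = 3.034, that is eta squared = 2 × 3.034/(2 × 3.034 + 237) = 0.025. An observed value between 0.01 and 0.025 counts as at least small in Step 1 but is not significant on that test. Under the written rule, eta squared ≥ 0.01 with both a's null occurs in 32% of the AS-midway trials, and in 21% of trials with truly equal arms. It is therefore not evidence of a difference either.

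**How large a CT–MM gap can go untested.** Each contrast is non-significant up to t(.975, 237) × √(2/80) = 0.3115 SD. At a1 = +0.3115 and a2 = −0.3115, CT − MM = 0.623 SD, t = 3.94, p = 0.0001 and eta squared = 0.061. This is the limiting case.

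**The case against.** The strongest reply is that most of this is wording. Item (4) says the two coefficients are to be read together, the plan counts one between-group question per mechanism, c1 and c2 are explicitly combined, and Table 5 matches 2 df. A joint test was probably intended. That is fair, but the operative sentence says either or both. Figure 3 is not shown in the text available, so it cannot settle the matter.

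The 9% rate also does little harm to Specific conclusions, which further require a significant b and post hoc tests favouring the targeted arm. If both post hoc contrasts must favour that arm, a false Specific pattern on the a-part with equal arms occurs in about 0.5% of trials per mechanism under the written rule and 0.4% with a 2-df gate. With CT truly 0.5 SD better, support is 80.6% against 80.2%. Nor can the untested CT–MM contrast hide a Specific result, since each Hypothesis 1c prediction includes at least one contrast with AS. This stands: the exposure is on the Shared side.

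The joint test also does not cure weak nulls. In the patterns Hypothesis 1c predicts it misses about as often as the written rule, and more often when only AS differs. AS midway is not a predicted pattern, and both a's null with an observed CT–MM gap above 0.55 SD occurs in only 1.7% of those trials. This stands too, and it is why intervals and cautious wording matter more than the choice of test.

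Finally, Step 1 does give an effect-size reading from a three-arm ANOVA. It is not carried into the Step 2 verdict, which the plan assigns to significance levels.

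**Conclusion.** The concern holds and should be fixed. The rule for the primary question words a null as similarity without the smallness that Hypothesis 1b requires, leaves CT versus MM untested when both a's are null, and does not define which p-value enters the six-test alpha control. These defects lie in the text and do not depend on simulation.

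Their size does rest on the stated assumptions. For a one-arm difference of 0.3 SD, a null on the a-part occurs in 36–50% of trials under the written rule and 52% under a 2-df test. At 0.5 SD the figures are 4–11% and 9%. Clustering by treatment group and missing data are not modelled, and FIML may use more than 80 per arm. The main harm is an unsupported Shared Mechanisms conclusion; the effect on Specific conclusions is small.

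**What to change.** 1. Replace the either/or rule with one 2-df joint test of a1 = a2 = 0 per mechanism, and name it as the between-group test counted among the six. Label the dummies as contrasts with AS.
2. Report all three pairwise differences in early slope with confidence intervals, whatever the joint test shows.
3. Word a non-significant result as no between-treatment difference shown. Discuss similarity only in light of the effect size and intervals, in line with Hypothesis 1b.

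The cost is SAP wording and three intervals per mechanism, with no new data or sample. Shared conclusions become more cautious. The joint test is less sensitive than the written rule when only AS differs, partly because the written rule runs at 9% size.

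A formal equivalence bound is optional and for the sponsor to decide. A bound at the Step 1 cut, about 0.21 SD (one arm differing) to 0.25 SD (AS midway), could not be met at 80 per arm, where the 90% half-width for a pairwise difference is 0.26 SD.

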Chronic pain is a common and costly condition affecting millions of Americans, and spine pain (including back and neck pain) is the most common chronic pain condition. Although various psychosocial treatments are effective for chronic pain, there is a critical lack of research examining if these treatments work via the mechanisms specified by theory. Three of the most common components of pain treatments are: (1) Cognitive Therapy (CT); (2) Mindfulness Meditation (MM), and (3) Activation Skills (AS). Theoretically, CT targets unhelpful cognitions (cognitive content, i.e., pain catastrophizing), MM targets how patients think (cognitive process, i.e., non-judgmental awareness), and AS targets what people do (i.e., more “well” behaviors”). However, we do not know if these techniques are effective via these specific mechanisms, or via shared mechanisms. Knowledge concerning treatment mechanisms is critical for modifying treatments to focus on the mechanisms that have the greatest benefits for the most patients. Further, understanding the mechanisms underlying post-treatment maintenance of gains and relapse will advance capacity to optimize long-term beneficial outcomes.

Actigraphy and ecological momentary assessment (EMA) consisting of multiple daily measures allows for the evaluation of longitudinal mechanism effects. In the context of a clinical trial, use of actigraphy and EMA data could determine the specific lag times of mechanism effects (i.e., how long it takes for a change in a mechanism to influence key outcomes). Thus, utilizing actigraphy and EMA throughout a controlled trial represents an innovative approach to assessing psychosocial pain treatment mechanisms at a micro-level.

A2. Specific Aims and Hypotheses

In the planned trial, 300 individuals with chronic pain including low back pain as a primary or secondary pain problem will be randomly assigned to telehealth-delivered CT, MM, or AS. Mechanisms and outcomes will be assessed with actigraphy and twice daily EMA during baseline, treatment, and for 4-weeks post-treatment. Mechanisms of longer-term maintenance of gains will be evaluated at 3- and 6-month follow-up. Given past research showing equivalent efficacy for active treatments, we expect no significant group level outcome differences between conditions. However, we do expect *individual* variability in treatment response and maintenance of gains that will allow us to examine mechanisms of change. This study will address two aims.

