At the end of the study when it comes time to conduct data analysis, study investigators (including those unblinded to intervention, such as both co-PIs) may need access to the data, in order to conduct specific analyses. Since (1) no investigators would be able to link any individual participant whose name was heard in fidelity recordings to any study data, and (2) any data investigators (blinded or unblinded) have access to at this point in the project would be locked, it is thus possible for unblinded investigators to also partake in data analysis.

Any staff member listed above may, with discretion from the co-PIs, participate in the actual writing/editing portion of any manuscript(s) that result from this study. During the data collection

phase of the study, blinded staff will not analyze or report data. Once the data is locked, all staff members, unblinded or blinded, may assist with analyzing or reporting data as needed.

D6s. Statistical Analyses

Structural equation modeling (SEM) will be used to evaluate the extent to which early treatment changes in catastrophizing, activity level, and non-judgment predict subsequent late treatment changes in pain interference, and the extent to which these associations are shared across the three treatments, or if some are unique to a subset of the treatments (Aim 1). We will also use SEM to examine the mechanisms of maintenance of gains from post-treatment to follow-up, to address the secondary study aim. Relevant covariates will be tested for and appropriately controlled for (when indicated) across all models. The Hochberg and Benjamini procedure will be used to control for alpha inflation in all analyses. This alpha control procedure involves putting the significance levels of the planned primary analyses in ascending order, and matching them to the actual significance levels obtained with the analyses, also placed in ascending order.

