Figure 3 below represents the initial model we plan to test for the catastrophizing mechanism variable, providing that it evidences at least a small effect for change for at least one treatment condition during the first two weeks of treatment. However, the model will be simplified (by removing treatment condition as a predictor, and the paths associated with treatment condition) if non-significant treatment effects are found. Up to two additional SEM models will also be tested, with non-judgment and activity level as the foci. Below we describe the specific steps planned to address the study aims and test the primary study hypotheses.

Figure 3. Initial model testing the mechanism role of pain catastrophizing during treatment

Step 1. Ensure at least small time effects (slope) in the early mechanism variables for at least one of the treatment conditions (a requirement for that variable to be considered as a possible mechanism).

- (1) We will perform an initial one-way Analysis of Variance (ANOVA) comparing the pre- to mid-treatment mechanism slopes between the three treatment conditions, separately for each of the three mechanism variables, with a goal of identifying the effect (i.e., Eta squared, η^2) associated with any between group differences in early changes in mechanism variable. If this effect size is < 0.01 , this would indicate a less than small between-group difference in the amount of early treatment change for that mechanism;

this would be interpreted to mean that all three treatment conditions had a similar effect on early treatment change in the mechanism variable.

- (2) In the event that a less than small between condition effect is found, we would then examine the pre- to mid-treatment time effect of this mechanism collapsed across groups to see if this mechanism changes from pre- to mid-treatment (i.e., early treatment). If this effect size (η^2) associated with this time effect collapsed across groups for any mechanism variable is less than 0.01 (representing a small time effect) then there would be evidence that the variable in question is unlikely to act as a mechanism, because at least some change over time early in treatment for that variable, on average, is needed for it to serve as a mechanism.

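### Step 2 takes treatment condition out of the SEM when a1 and a2 are both non-significant, so the b coefficient behind a Shared verdict is not adjusted for randomised arm

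*Combined protocol and SAP*

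**What the plan says.** All of this is in D6s, Statistical Analyses.

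- **Introduction to Figure 3:** "the model will be simplified (by removing treatment condition as a predictor, and the paths associated with treatment condition) if non-significant treatment effects are found".
- **Step 2, item (4):** "First paths a_1 and a_2 will be tested". Then: "If both of these coefficients are non-significant (consistent with the Shared Mechanisms Model) they will be eliminated from the final SEM".
- **Step 2, item (6):** after the a-path decision, "we will next test for significance of the *b* coefficients".
- **Paragraph after item (6):** the finding that supports the Shared Mechanisms Model is "A significant *b* coefficient in light of non-significant *a* coefficients".
- **Footnote to Step 2:** arm is coded by two dummies, CT versus other and MM versus other. With both in the model, AS is the reference, so a1 is CT minus AS and a2 is MM minus AS.

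Nothing in D6s puts arm back into the model for b once it has been removed. The only general provision is that relevant covariates are controlled for when indicated, and arm is not named among them. In A2 the investigators write that "we expect no significant group level outcome differences between conditions". D6u gives 240 analysed participants, 80 per arm, and bases its power argument on models that include treatment condition as an interaction.

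**The concern.** Randomised arm can influence both early mechanism change and late change in pain interference. If it does and is left out of the outcome equation, b mixes the within-arm association, which is what the trial wants, with differences between arm means. The rule removes arm because two tests were not significant, which does not show that the arms are alike. The three mechanisms may also end up tested in differently specified models, chosen by the data.

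The Shared or Specific conclusion of the primary aim rests on this step. A b distorted upwards could support a Shared mechanism that is not there. A b distorted downwards could miss one that is.

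**Working it through.** **1. The plan's own figures (Table 5).** The interaction rows use f² = 0.15 and power 0.80. A noncentral F calculation with two tested predictors gives 93, 98 and 102 at alpha 0.013, 0.010 and 0.008, exactly as printed. One tested predictor gives 77, 82 and 85. For the mediation rows, joint significance at r = 0.30 with Fisher's z gives 112, 131 and 142 against 109, 129 and 140 printed, a close match. The interaction rows therefore fit a two-df treatment term, so the power argument has arm in the model while Step 2 may delete it.

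**2. How weak the pretest is.** Inputs: 80 per arm (D6u) and two-sided 0.05, which is assumed because item (4) names no level. The largest non-significant coefficient, in SDs of the early slope, is

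t(.975, 237) × √(2/80) = 1.970 × 0.158 = 0.311.

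With a1 and a2 at this limit and of opposite sign, CT and MM differ by 2 × 0.311 = 0.62 SD, and neither dummy tests that contrast. Power for CT versus AS is 47.5% at 0.3 SD; 80% power needs 0.44 SD.

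**3. When b is biased.** Take unit within-arm variance of the early mechanism slope and within-arm slope b. Let B be the variance of the arm means of the mechanism, and C their covariance with the arm means of late interference. Without arm in the outcome equation, b tends to

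(b + C) / (1 + B).

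This equals b if the arms do not differ on the mechanism (B = C = 0). It also equals b if arms differ late only through the mechanism (C = bB). Bias therefore needs arm differences on the mechanism and, apart from what the mechanism transmits, on late interference.

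Examples with b = .20 and late means of equal size and opposite sign:
- CT +.25, MM −.25, AS 0: B = (2 × .0625)/3 = .042, C = −.042, giving (.20 − .042)/1.042 = .152.
- CT +.25 alone: B = .0625 × 2/9 = .014, C = −.014, giving (.20 − .014)/1.014 = .183.

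In trials that pass the pretest the observed differences are smaller, so the bias is somewhat less, as the simulation shows.

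**4. Simulation of the rule.** 80 per arm; arm dropped if a1 and a2 both have p > .05; b tested at .05 unless stated. The arm means are assumptions.

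| Assumed arm means (SD) | True b | Trimmed trials: arm out v arm kept | All trials under the rule |
|---|---|---|---|
| No differences | .20 | power 87.8% v 88.0% | no loss from keeping arm |
| One arm (CT) +.25, late opposite | .20 | b .188 v .200; power 84% v 88% | – |
| CT and MM ±.25, late opposite | .20 | b .163 v .199; power 72% v 88% | power 81% v 87% |
| CT and MM ±.30, late opposite | .20 | b about .15 v .20; power 66% v 88% | – |
| One arm leading by .25–.30, late same direction | 0 | false positives about 5.3% v 5% | about 5.1% |
| CT and MM ±.25, late same direction | 0 | false positives about 7% v 5% | 5.7% |
| CT and MM ±.30, late same direction | 0 | false positives about 9% v 5% | 6.0% |

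The rule trims about 35% of trials at ±.25 and about 20% at ±.30. In 72% of the trimmed trials at ±.25, CT and MM differ at p < .05. Repeat runs moved most cells by up to about 3 points; the 66% cell ranged from 61% to 66%. Larger late differences raise the figures: with mechanism means ±.30 and direct late effects up to ±.50, false positives reach 14.7% in trimmed trials and 6.7% over all trials.

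**5. At the planned effect, r = .30.** In the ±.25 scenario, power in trimmed trials is 98.4% with arm out and 99.6% with arm kept. In the ±.30 scenario at alpha .0083, the lowest case found, it is 87% v 98%.

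**The case against.** **Figure 3 is not shown.** Item (4) alone removes only the paths into the mechanism. With observed slopes, that does not change b, which comes from the outcome equation. Trimming alters b only if the figure had an arm path to late interference that the simplification then removes. A reader might infer that trimming is what leaves b unadjusted. The documents do not establish this: without such a path, b was never adjusted in either branch. This stands, and the point is worded to cover both cases.

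**The larger figures come from an adverse layout.** CT and MM lie on opposite sides of AS, late slopes also differ, b is .20 rather than the planned .30, and only trimmed trials are counted. The Specific model in A2a has one arm leading on each mechanism, and there the effect is small. This also stands, which is why a range is given.

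**Early interference may be in the model.** D6s computes early slopes for the outcome too. If late arm differences arise through early interference and that term is in the SEM, the bias nearly vanishes (b .193 v .199, power 86% v 87%). That cannot be checked without the figure.

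**Two stronger readings are not supported.**
- *That the rule is circular.* D6s ranks the p values of the planned tests, "matching them to the actual significance levels obtained with the analyses, also placed in ascending order", so significance of a could depend on the p value for b. But item (4) names no alpha for trimming, and an unadjusted .05 would not be circular.
- *That equal overall outcome forces late arm differences against b.* A2 states only an expectation about group outcomes. The argument concerns early versus late interference, whereas bias also needs arm differences in the mechanism. Bias in that direction would weaken b rather than produce a false Shared verdict.

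**Conclusion.** The concern holds in a limited form. As written, b in the Shared branch is not adjusted for randomised arm, and the test used to justify this would miss CT or MM differing from AS by up to 0.31 SD, and CT differing from MM by up to about 0.6 SD. Whether the pretest causes the lack of adjustment depends on Figure 3.

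The harm is conditional. It is nil unless arms differ on the early mechanism and also, other than through it, on late interference. It is negligible with one leading arm and moderate within trimmed trials when CT and MM lie on opposite sides of AS. It is small over all trials in the main scenarios, and power at the planned r = .30 is not threatened. These sizes rest on assumed arm means, normal slopes, two-sided .05 for trimming, and no allowance for therapy-group clustering or baseline-slope covariates. The documents do not support saying that b will be materially biased. The case for change is that the protection is almost free and applies to the primary-aim model.

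**What to change.** In D6s, delete the simplification sentence introducing Figure 3 and the elimination rule in Step 2, item (4). In all three SEMs, keep both arm dummies with paths to the early mechanism slope and to the late pain-interference slope, whatever their p values. Take every a and b p value from these fixed models and apply the alpha procedure once. Report a1, a2 and a1 − a2 with confidence intervals beside b, so that the CT versus MM contrast is visible. Reconcile the text with D6u, which already assumes that treatment condition is in the models.

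The cost is SAP wording and two degrees of freedom per equation out of about 240. With no arm differences, keeping the dummies leaves power essentially unchanged (88.0% v 87.8% at b = .20).
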